6. RANDOMIZATION

A web-based central randomization system will be developed by the SDMC and installed on the WebDCU™ SHINE study website using a combination of covariate balance and response-adaptive randomization (RAR) method.⁶ The randomization design is aimed to preserve the randomness of treatment assignment, prevent serious imbalance in important baseline prognostic variables and promote subject recruitment while preserving the statistical test power. In summary, the probability of treatment assignment under the proposed scheme will be based on the prevention of serious imbalance in the pre-specified prognostic variables and the favorable outcome rate of each treatment arm. The specific prognostic variables at the time of randomization are: baseline NIHSS strata (3-7; 8-14; 15-22); use of IV thrombolysis (Y/N); and, site. Favorable outcome will be based on the baseline severity adjusted dichotomized mRS as previously described.

The SHINE Randomization algorithm will be fully detailed and documented in the SHINE Randomization Plan and Validation Documents. These documents will be developed prior to the enrollment initiation and stored in a secure location at the SDMC. The documents will be archived with the study database at the end of the trial. In summary, the trial will start with a 1:1

allocation scheme focusing on covariate balance. The RAR will be implemented once an adequate amount of primary outcome information is collected. With RAR, each enrolling subject will have a higher probability (greater than 50% chance) of being assigned to the treatment arm with the higher success rate based on previous subjects' responses. The SDMC's computer system will run both the 1:1 allocation and the RAR. Participating sites and members of the study team will not notice any difference between the randomization schemes and sites will only need to press one randomization button on the computer screen to obtain the assigned treatment during the course of the study. To ensure proper randomization, the unblinded statistical programmer will have access to the randomization information in order to oversee the quality control of the computer program.

7. BLINDING

The study is conducted in a single blind manner with double blind outcome assessment. The site treatment team will be unblind to treatment assignment however the study subject and 90-day outcome assessor are both blind to the treatment assignment. Treatment allocation is concealed and subjects will not be told of their actual treatment until the trial completion unless emergency unblinding is required.

The SDMCs unblinded staff will produce two identical sealed envelopes that contain identification of treatment codes. Prior to initiation of the Trial, one envelope of (2) is given to the NINDS Liaison to the DSMB. Another is maintained in a locked file cabinet at the SDMC in its limited access central file room.

The DSMB is partially unblinded for the closed reports (data reported by A and B only). However, if it so wishes, it may be completely unblinded at any time during the Trial. If the DSMB wishes to be unblinded on a particular subject only, the NINDS Liaison to the DSMB should email the request to the unblinded SDMC biostatistician.

8. MISSING DATA

Under the ITT principle, all subjects who are randomized are included in the analysis. Although every attempt will be made to prevent incomplete data, a certain amount of missing data is inevitable due to losses to follow up or withdrawn consents. The investigators also need to consider primary outcome data that is collected late (i.e., past the pre-specified data entry timelines of +/-14 days). Based on discussions with the SHINE Executive Committee and clinical expertise, primary outcome data (i.e., 90-day mRS) collected past the data entry timelines will only be used for the primary analysis if the collection falls within -14 days/+30 days from the scheduled date. Data collected outside the 30-day window (only allowed up to 180 days to collect data) will be considered missing for the primary outcome.

A thorough analysis of variables, reasons and patterns of missing data will be conducted. Based on other large acute stroke trials that capture 90-day mRS, we anticipate no more than a 3% lost to follow up rate. At the time of each planned analysis (interim and final), the unblinded statistician will report the amount of missing primary outcome data. Multiple imputation using SAS PROC MI and MIANALYZE will be used to impute the missing 90-day mRS outcome data. In summary, 5 imputed data sets will be generated using PROC MI. The imputation model will include the primary analysis variables (90-day mRS, treatment, baseline NIHSS, thrombolysis use) plus age, gender and 6-week mRS. Each imputed data set will be analyzed according to the specified primary analysis (Section 10.1.2) and MIANALYZE will be used to combine the

results from the multiple imputed data sets to obtain a single set of parameter estimates. The multiple imputation method assumes missing at random (MAR) which means that the probability of missing outcome data can depend on the observed values of the individual but not on the missing values of the individual. Although we anticipate minimal missing data, sensitivity analyses will be conducted to assess the impact of any bias due to missing data. The primary analysis will be re-run using the following methods:

- Complete case analysis (only those with 90-day outcome)
- Worst case analysis (assume any subject with missing 90 day outcome to be considered a 'failure')
- Inclusion of primary outcome data collected outside the defined window

If the treatment effect is robust, we expect these sensitivity analyses to yield similar inferences, particularly if the missing data are minimal (~3%). Any discrepancies between the sensitivity analyses and the primary analysis results will be investigated to understand the reason for the discrepancy.

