9. DISCONTINUATION OF PARTICIPATION

9.1 Subject Removal from Therapy

As participation in the SHINE trial is voluntary, the subject or LAR may decline study therapy at any time. In addition, the treating physician may stop the study therapy if there is a safety concern. The subject will continue to be followed through the 90 Day visit unless informed consent is withdrawn.

^{**}Completion of 72 hr treatment period unless discharged prior to 72 hrs

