9.2 Subject Withdrawal

The subject has the right to voluntarily withdraw from the study at any time for any reason without prejudice to his/her future medical care by the physician or at the institution.

For the occasional subject who withdraws consent, the date and reason for consent withdrawal should be documented. Subject data will be included in the analysis up to the date of the consent withdrawal.

A distinction will be made between subjects who fail to complete all forms on schedule or who miss some follow up assessments and the withdrawal of consent. Missed or rescheduled visits will be documented, but the subject will continue to be followed in the future according to protocol requirements, and all follow-up data will be included in the analysis.

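### Subjects lost between end of treatment and 6 weeks have their 90-day mRS imputed from treatment and baseline data alone, although an end-of-treatment NIHSS is scheduled for everyone

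*SAP*

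**What the plan says.** **Window.** Under SAP section 8, a 90-day mRS obtained late "will only be used for the primary analysis if the collection falls within -14 days/+30 days from the scheduled date". Collection may continue beyond that, but "Data collected outside the 30-day window (only allowed up to 180 days to collect data) will be considered missing for the primary outcome".

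**Imputation.** Missing 90-day scores are handled by multiple imputation: "5 imputed data sets will be generated using PROC MI". The variables are listed: "The imputation model will include the primary analysis variables (90-day mRS, treatment, baseline NIHSS, thrombolysis use) plus age, gender and 6-week mRS". The section assumes missing at random and expects a loss to follow-up of at most 3%.

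**Sensitivity analyses.** The primary analysis is re-run on complete cases, with all missing outcomes counted as failures, and with late scores: "Inclusion of primary outcome data collected outside the defined window". Discrepancies from the primary result are to be investigated.

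**What is collected.** Protocol section 8.1.4 requires the NIHSS at least daily during treatment. Table 5 in protocol section 8.7 also lists it at completion of treatment or discharge, a time point that its footnote defines as "Completion of 72 hr treatment period unless discharged prior to 72 hrs". The same table schedules the mRS only at 6 weeks and at 90 days.

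**Withdrawals and missed visits.** Protocol section 9.2 keeps a withdrawing subject's data up to the date of withdrawal. After missed or rescheduled visits, the subject stays in follow-up and "all follow-up data will be included in the analysis".

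**The concern.** Missing at random lets the chance of a missing outcome depend on what was observed for that subject. That helps only if the observed predictors are in the imputation model. For a subject who withdraws or is lost after treatment but before 6 weeks, the listed model has nothing observed after baseline. The 6-week mRS is missing too, so it adds no information for that subject. The severity of the deficit at the end of treatment is an obvious candidate predictor of both staying in the trial and the 90-day result, and it is left out.

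If early leavers had recovered worse than their baseline data suggest, they would be imputed too favorably. If this happened to a different degree in the two arms, the primary comparison would shift. The treating teams know the assignment (protocol section 8.2.2, SAP section 7), so a difference between arms is possible. Nothing in the documents shows that it occurs.

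**Working it through.** **1. Design figures, reproduced first.** The inputs come from SAP section 4.1: 25% versus 32%, two-sided alpha 0.05, power 80%. For two independent proportions with pooled variance under the null, the mean rate is 0.285, and

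n per arm = [1.960 × √(2 × 0.285 × 0.715) + 0.842 × √(0.25 × 0.75 + 0.32 × 0.68)]² / 0.07² = 652.

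The total is 1304, against the stated 1314. Simulated power with the stated group-sequential boundaries is 78.5% at 1314 and 81.0% at 1400, against 80% in SAP section 4.1 and 81% in Appendix A. The design figures hold, and the missing-data rule does not alter them.

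**2. What the imputation can draw on.**

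| Subject | Usable under the SAP list | Scheduled but not in the list |
|---|---|---|
| Lost or withdrawn after treatment, before 6 weeks | treatment, baseline NIHSS, thrombolysis, age, gender | end-of-treatment NIHSS |
| Reached the 6-week call, nothing later | the above plus 6-week mRS | end-of-treatment NIHSS, which adds less here |
| Seen only after the +30-day limit | the above, plus 6-week mRS if the call was made | end-of-treatment NIHSS (the late mRS is unscheduled and also not in the list) |

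The first row is the gap. For these subjects, the complete-case analysis drops them, the failure analysis gives them all the same value whatever was observed, and the late-score re-run has no score to add.

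**3. Whether the two omitted measurements could be used.** The end-of-treatment NIHSS is scheduled for all subjects, so most will have both it and an in-window 90-day mRS. Its relation to the outcome can be estimated from the trial. A late mRS differs. No subject is scheduled to have both a late and an in-window score, so PROC MI has no pairs from which to estimate how one predicts the other.

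**4. Size of the bias.** Let q be the fraction of outcomes imputed in each arm, and e the imputed minus the true favorable rate among them. The error in an arm's rate is q × e. With the same q in both arms, the bias in the risk difference is q × d, where d is the difference in e between arms. The documents give neither the fraction lost before 6 weeks nor d, so both are assumed. Taking q = 3% sets it at the SAP's ceiling for loss to follow-up, as if every loss came before 6 weeks.

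| q | Subjects of 1400 | d = 5 points | d = 10 points | d = 20 points |
|---|---|---|---|---|
| 1% | 14 | 0.05 | 0.10 | 0.20 |
| 3% | 42 | 0.15 | 0.30 | 0.60 |
| 5% | 70 | 0.25 | 0.50 | 1.00 |

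The entries are percentage points. At 3% they amount to 0.15/7 = 2% up to 0.6/7 = 9% of the target difference. Imbalance in missingness also matters. With 5% missing in one arm, 1% in the other and the same error e of 5 to 20 points in both, the bias is (0.05 − 0.01) × e = 0.2 to 0.8 points.

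**5. Precision.** If the affected subjects contributed nothing, fixed-design power at 1400 would fall from 82.7% to 82.4%, 81.6% and 80.8% at 1%, 3% and 5%. Five imputations are enough: at 3% missing information, relative efficiency is 1/(1 + 0.03/5) = 99.4%.

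**The case against.** The plan is not careless here. It includes the 6-week mRS, a later measure on the outcome scale itself, so the gap concerns only subjects lost before that call. It calls for a study of the reasons for and patterns of missing data. The failure analysis covers the case in which every lost subject did badly. A link between early recovery and withdrawal, given the listed variables, is conjecture. All of this stands, and it is why the point is an improvement rather than the repair of an error.

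The remedy also has a cost. Protocol section 8.1.4 only recommends a certified rater for the in-hospital NIHSS, and nothing says that the rater is blinded. Protocol section 8.6 has the 6-week call and the 90-day assessment done by a blinded investigator. Adding the NIHSS could bring unblinded ratings into the imputation of the primary outcome. This is a fair caution but a limited one. Treatment is already in the imputation model, so its coefficient absorbs a constant rating shift between arms. A shift that varied with severity would not be fully absorbed.

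Two stronger readings are tempting:

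- **The late-score rule breaks the protocol.** A reader might infer this from section 9.2. That section separates missed visits from withdrawal of consent and names neither the primary analysis nor a window. Protocol section 12.2.1 leaves analysis details to the SAP, a pre-specified window is legitimate, and late scores do enter a planned analysis. The two texts need reconciling; there is no broken commitment.
- **The late mRS belongs in the imputation model.** Step 3 shows why this fails without an outside assumption.

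A reader might also judge the harm by how often an imputed value differs from a subject's true one. Multiple imputation does not aim to recover individual values, and such a count is not bias in the treatment effect.

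**Conclusion.** The concern holds in a limited form. For subjects lost between the end of treatment and 6 weeks, the listed model ignores a scheduled post-treatment severity score, and no listed sensitivity analysis makes up for that. The likely bias is about 0.15 to 0.6 percentage points against the 7-point target. This assumes that 3% of outcomes are affected and that the imputation error differs by 5 to 20 points between arms. Adding the NIHSS would reduce this only as far as the score explains the difference. The trial's conclusion is unlikely to turn on it unless missing data are well above the SAP's expectation or unequal between arms. The handling of late scores is acceptable as planned and needs only consistent wording in the two documents.

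**What to change.** 1. **SAP section 8:** add the end-of-treatment/discharge NIHSS to the PROC MI model as an auxiliary variable, and state what is used when that score is itself missing. The primary analysis model, the window and the three sensitivity analyses stay as they are.
2. **SAP section 8:** acknowledge that in-hospital NIHSS ratings may be unblinded and that treatment remains in the imputation model for this reason among others.
3. **Protocol section 9.2:** state that mRS scores obtained outside the SAP window enter the pre-specified sensitivity re-run and not the primary analysis. Do not add late scores to PROC MI.

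The cost is a few sentences and one already scheduled variable in the imputation code, with no new data collection. The change should be fixed before anyone who decides on it has seen outcomes by arm. Because SAP section 8 applies to interim as well as final analyses, it is best made before the first interim look.

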10.1.2 Primary Efficacy Analysis at the End of the Trial

The primary outcome analysis of the 90-day mRS will use a stratified dichotomy methodology for assessing improvement as defined in the Primary Outcome section above. Outcome differences will be analyzed under the intention-to-treat principle, therefore all randomized subjects will be included in the primary analysis sample. To assess efficacy, the treatment groups will be compared with respect to the proportion with favorable outcome 90 days post randomization after controlling for the variables included in the randomization scheme. The primary statistical analysis will develop a generalized linear model using the PROC GENMOD procedure in SAS® v9 with treatment group as the factor of interest and baseline NIHSS strata (3-7, 8-14, 15-22) and thrombolysis use (Yes/No; includes both IV and IA therapies) as covariates. A Wald

[figure not shown]
chi-square test will be performed to compare the treatment group proportions using a two-tailed significance level of 0.05. Adjusted relative risks will be reported with two-sided 95% confidence intervals. Additional analyses will identify potential confounding (prognostic) variables to be used as covariates in subsequent secondary analyses of the primary outcome. Specific covariates include age, gender, race, ethnicity, admission blood glucose, previous stroke, lacunar subtype, and time between stroke onset and treatment. If statistically significant differences are evident, then post-hoc analyses will be conducted to determine if differences had an effect on the conclusions from the pre-specified primary analysis.

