10.1.3 Interim Analysis Plan

The study is designed using four interim looks for both efficacy and futility of the primary outcome and one final look for a total of 5 planned analyses of the primary outcome. The interim analysis plan uses the error spending function method with O'Brien and Fleming (OBF) type stopping guidelines⁷⁻⁹. The error spending function distributes the type I and II error rates across the interim monitoring points giving the flexibility of changing the intervals of monitoring while still preserving the overall type I and II error rates. The OBF-type boundary is considered conservative as its boundaries make it difficult to terminate a study early on by requiring extreme early evidence of efficacy or futility. It spends smaller amounts of alpha at the first look and gradually increases the spending as more information is acquired. The trial may be stopped for overwhelming efficacy of one treatment group over the other or for futility at the planned interim analyses if the test statistic crosses the respective boundaries.

The current plan is to conduct the first interim analysis after approximately 500 randomized subjects complete the primary outcome assessment (90-day mRS). Assuming an accrual rate of 33.3 patients per month, it is anticipated that the 1st look will occur roughly 2.5yrs from the start of enrollment. Subsequent analyses will occur after every additional 200 subjects complete the 90-day mRS (i.e., 700, 900, and 1100). The interval may be altered if requested by the DSMB. The stopping boundaries are defined using the gamma family spending functions with a gamma value of -4 (closely resembles OBF boundaries)¹⁰. Specific to the futility boundaries, they are derived as non-binding meaning that if a futility boundary is crossed there is the ability for it to be overruled without inflation of the type 1 error rate. If the crossing of an efficacy boundary is overruled, then this decision can impact the type II error rate but not the type I error rate. EAST[®] 5 software (Cytel Corporation) was used for the boundary calculations.

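### The primary test pools only 5 imputations with no stated seed, which leaves avoidable random noise of about 0.05–0.08 SD in the final Z

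*SAP*

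**What the plan says.** SAP Section 8 makes multiple imputation the method for missing 90-day mRS under intention to treat: "In summary, 5 imputed data sets will be generated using PROC MI". The imputation model holds the primary-analysis variables plus age, gender and the 6-week mRS. Each completed data set receives the Section 10.1.2 analysis, and MIANALYZE pools the results. In that analysis a Wald "chi-square test will be performed to compare the treatment group proportions using a two-tailed significance level of 0.05". Section 10.1.3 sets the final critical value at Z = 2.02 (p = 0.043).

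On the amount of missing data, Section 8 says "we anticipate no more than a 3% lost to follow up rate". Separately, an mRS collected outside −14/+30 days "will be considered missing for the primary outcome", so late assessments can add to the 3%. For the looks, the section says: "At the time of each planned analysis (interim and final), the unblinded statistician will report the amount of missing primary outcome data". It lists three sensitivity analyses: complete case, worst case, and inclusion of out-of-window data. The SAP text states no seed, no rule for raising the number of imputations, and no report of Monte Carlo error.

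**The concern.** A pooled estimate from m imputations keeps some random error because m is finite. That error comes from the random-number stream and carries no information about treatment. With m = 5 it is large enough to be visible in the p-value: the same locked data set, run with two seeds, can give two different answers. At the final look a single cut-off, Z = 2.02, separates rejecting the null from not rejecting it. If the result falls close to it, the trial's conclusion depends partly on a choice that the plan leaves open, which pre-specification is meant to prevent.

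**Working it through.** **Inputs from the SAP.** m = 5 and at most 3% missing (Section 8). Rates of 25% and 32% (Section 4.1). Looks at 500, 700, 900, 1100 and 1400, with the tabulated boundaries (Section 10.1.3). **Assumed.** A fraction of missing information (FMI) of 1.5–3%. It should not much exceed the missing proportion, and it falls as the 6-week mRS becomes more predictive.

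**1. Reproduce the plan's boundary.** Section 10.1.3 says: "The stopping boundaries are defined using the gamma family spending functions with a gamma value of -4". Spending a two-sided 0.05 this way over the five looks gives 2.97, 2.86, 2.65, 2.42 and 2.02, the same as the SAP table. Simulating trials with the table's efficacy and futility boundaries gives power 0.807 and type I error 0.048. Appendix A reports 81% and 4.8%.

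**2. Seed noise by formula.** Given the data, the pooled estimate has Monte Carlo variance B/m, where B is the between-imputation variance. With FMI ≈ B/T and T the total variance, SD(Z) ≈ √(FMI/m).

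| FMI | m = 5 | m = 50 | m = 100 |
|---|---|---|---|
| 1.5% | √(0.015/5) = 0.055 | 0.017 | 0.012 |
| 2% | √(0.02/5) = 0.063 | 0.020 | 0.014 |
| 3% | √(0.03/5) = 0.077 | 0.024 | 0.017 |

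Relative efficiency at m = 5 and FMI 3% is 1/(1 + 0.03/5) = 0.994, a loss of about 0.6%.

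**3. Seed noise by simulation.** Settings: N = 1400, logistic imputation with parameter draws, a log-link model with NIHSS strata and thrombolysis, Rubin pooling, and 30 seeds for each of 12 data sets. The table shows the SD of Z across seeds.

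| Missing | 6-week predictor | m = 5 | m = 50 |
|---|---|---|---|
| 3% | none | 0.079 | 0.024 |
| 3% | moderate | 0.066 | 0.020 |
| 3% | strong | 0.054 | 0.018 |
| 5% | none | 0.108 | 0.035 |
| 5% | moderate | 0.088 | 0.030 |
| 5% | strong | 0.073 | 0.023 |

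Formula and simulation agree. The simulation imputes the favorable/unfavorable outcome directly, whereas the SAP imputes the mRS.

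**4. Near the boundary.** One SD of 0.08 around 2.02 spans Z = 1.94 to 2.10, or p = 0.052 to 0.036. If the noise-free Z lies a distance g from 2.02, one seed puts the result on the other side with probability Φ(−g/SD):

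| g | m = 5 (SD 0.055–0.079) | m = 50 (SD divided by √10) |
|---|---|---|
| 0.05 | 18–26% | 0.2–2.3% |
| 0.10 | 4–10% | under 0.1% |
| 0.15 | 0.3–3% | under 0.1% |

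**5. Over all trials.** The expected final Z at 7 points is 0.07/√(0.285 × 0.715 × 4/1400) = 2.90. Two million trials were run through the SAP boundaries. Two independent seed errors were then added to each final Z, with SD 0.055–0.077, and disagreements about 2.02 were counted.

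| True difference | Trials reaching the final look | Seeds disagree, % of final looks | Seeds disagree, % of all trials |
|---|---|---|---|
| 7 points | 34% | 3.8–5.4 | 1.3–1.8 |
| 5 points | 46% | 4.2–5.9 | 1.9–2.7 |
| 0 | 25% | 2.0–2.9 | 0.5–0.7 |

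**The case against.** The strongest reply is that nothing here is invalid. Rubin's total variance includes the (1 + 1/m) term, so the finite-m noise is already in the standard error. The loss of FMI/m = 0.006 equals about 0.006 × 1400 ≈ 8 subjects. Seed flips go in both directions, so power hardly moves. The sampling SD of Z is about 1, and the seed adds at most about 0.6% to its variance at 3% FMI. All of this stands, and it limits the weight of the point.

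The complete-case and worst-case re-runs involve no random draws, and the SAP requires discrepancies with the primary result to be investigated. A knife-edge result might therefore be noticed. That is a partial safeguard: these runs answer other questions and do not measure seed dependence.

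Three stronger readings are tempting, and the documents do not support them.

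- **Every look is affected.** SAP Section 8 says only that the amount of missing data is reported at each look. The analysis it applies to the imputed data sets, Section 10.1.2, is headed as the end-of-trial analysis. Imputation at interim looks is a plausible inference, but it is not stated. The futility boundaries are also non-binding, and the DSMB and Executive Committee weigh safety and study progress as well.
- **The result could not be reproduced.** A recorded seed and program would reproduce it exactly. The problem is the arbitrariness of a single draw.
- **A large share of decisions would be wrong.** At a seed SD of 0.07, about 25% of results differ from the many-imputation answer, but only when the noise-free Z lies within 0.1 of the boundary. Differing from that answer is also not the same as differing from the truth.

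**Conclusion.** The point holds as a modest, avoidable weakness. At 3% missing, the pooled Z carries seed noise of about 0.05–0.08 SD. A final result within about 0.15 of 2.02 can turn on the seed, and at the 7-point effect this concerns about 1–2% of all trials. Type I error and power are not materially changed.

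The size rests on the assumed FMI of 1.5–3%. It sits at the lower end of the range if the 6-week mRS is strongly predictive and observed in those who miss day 90. It rises to about 0.07–0.11 if out-of-window assessments bring missing data to 5%. The change is worth making because it is specific and has no drawback, not because the planned test is unsound.

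**What to change.** In SAP Section 8:

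- Replace 5 imputations with 50 or more, for example 100. At 3% missing this lowers the seed SD to about 0.018–0.024 (m = 50, simulated) or 0.012–0.017 (m = 100, formula). Choosing 100 over 50 is a preference; either removes most of the noise.
- Pre-specify the seed. A seed alone gives reproducibility but only fixes one noisy draw, so it does not replace a larger m.
- State whether missing outcomes are imputed at the interim looks and, if so, apply the same number of imputations and the same seed rule there.

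Reporting the Monte Carlo error of the pooled Z would be a useful addition. The cost is one number, a sentence or two, and minutes of computing. Patients, sites, boundaries and sample size are not affected.

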4. SAMPLE SIZE DETERMINATION FOR THE PRIMARY EFFICACY OBJECTIVE

4.1 Sample Size Estimation

The primary outcome variable is the overall proportion of subjects experiencing a favorable outcome 90-days post randomization, where favorable is defined by the dichotomized mRS score as adjusted to the baseline NIHSS (stroke severity). Our preliminary data suggest a 25% rate of favorable outcome in the control group at 90 days is reasonable. A clinically relevant absolute difference in success rates between the two interventions is chosen as 7% (success rate_{control}=25%; success rate_{infusion}=32%). If the IV insulin group does not have at least a 7% or higher success rate than the control group, then IV insulin within 12 hours of symptom onset will not be considered a worthwhile therapy for hyperglycemic acute ischemic stroke patients.

Based on the above information and taking into consideration four planned interim analyses (see Section 10.1.4 for details), the study is powered to assure 80% likelihood of identifying a difference in success rates greater than or equal to 7%. Sample size estimation is based on the comparison of independent proportions adjusting for baseline NIHSS. The maximum sample size required for randomization is 1314 subjects (657/treatment group). Although every attempt will be made to avoid drop outs and losses to follow up, the required sample size is inflated for a 3% non-adherence rate. The total number of patients required for randomization is 1400.

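### The SAP's worst-case missing-data analysis counts missing as failure in both arms, so it does not bound the effect of missing outcomes on the treatment difference; a by-arm tipping-point table should be added

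*SAP*

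**What the plan says.** SAP section 8 (Missing Data) expects at most 3% loss to follow-up and gives no figure by arm. An mRS collected outside the window of 14 days before to 30 days after the scheduled date also counts as missing for the primary outcome. The primary analysis fills the gaps with five multiply imputed data sets under missing at random. The imputation model uses treatment, baseline NIHSS, thrombolysis, age, gender and 6-week mRS.

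The primary analysis is then re-run in three ways, to assess bias from missing data:
- complete case;
- "Worst case analysis (assume any subject with missing 90 day outcome to be considered a" failure, with no distinction by arm;
- inclusion of outcomes collected outside the window.

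The section continues: "If the treatment effect is robust, we expect these sensitivity analyses to yield similar inferences". It also promises to investigate any discrepancy, and to analyze the reasons for and patterns of missing data.

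Neither document contains an analysis that treats missing subjects differently by arm, a tipping-point analysis, or an imputation shifted away from missing at random.

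**The concern.** Failure is the worst outcome for a patient. Giving it to the missing subjects in both arms is not the worst case for a comparison between arms. For a claim that IV insulin is better, the worst case is that missing insulin subjects did badly and missing control subjects did well. No planned analysis looks in that direction.

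Missing at random cannot be verified from the observed data, so the sensitivity set has to probe it. The treating team knows the assignment (Protocol 8.2.2, SAP section 7), and SAP section 8 names withdrawn consent as a source of missing data. Loss that differs by arm in amount or in kind is therefore possible. At stake is what a final report may claim: a result described as having survived a worst-case analysis may have met little more than a repeat of the complete-case analysis.

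**Working it through.** **Inputs**
- Control rate 25%: "Our preliminary data suggest a 25% rate of favorable outcome in the control group at 90 days is reasonable" (SAP 4.1).
- Effect 7 points, so 32% on insulin: "A clinically relevant absolute difference in success rates between the two interventions is chosen as 7" percent (SAP 4.1).
- Test: a Wald "chi-square test will be performed to compare the treatment group proportions using a two-tailed significance level of 0.05" (SAP 10.1.2). The final boundary is Z = 2.02 (SAP 10.1.3).
- Total 1400, taken as 700 per arm. This is an assumption, because allocation becomes response-adaptive (SAP section 6).
- Missing 3% = 42 of 1400. A 21/21 split is assumed first, then others.

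**The plan's own figure.** "The maximum sample size required for randomization is 1314 subjects (657/treatment group"). The two-proportion formula, with mean rate 0.285, gives

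n = [1.96·√(2·0.285·0.715) + 0.842·√(0.25·0.75 + 0.32·0.68)]² / 0.07² = 652 per arm, or 1304.

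This is within 1% of 1314. Then 1314/0.97 = 1355 and 1314/0.97² = 1397, the latter matching 1400. A simulation with the SAP's five looks and listed boundaries gives 81.0% power at 1400, and Appendix A states 81%. The design values are sound, and the sample size does not depend on this point.

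**Why the all-failure rule is nearly neutral when missingness is equal.** If a fraction m is missing in each arm, both rates are multiplied by (1−m). The relative risk is unchanged. Z is multiplied by √[(1−p̄)/(1−(1−m)p̄)], where p̄ is the mean observed rate: √(0.715/0.7236) = 0.994.

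**Equal split, 21 missing per arm.** Expected favorable among the 679 observed: 0.25·679 = 169.75 control and 0.32·679 = 217.28 insulin. Unadjusted pooled Z:

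| Rule for missing | Control | Insulin | Difference | Z |
|---|---|---|---|---|
| Complete case (n = 679) | 25.0% | 32.0% | 7.0 points | 2.86 |
| All failure (n = 700) | 24.25% | 31.04% | 6.8 | 2.84 |
| Insulin failure, control favorable | 190.75/700 = 27.25% | 31.04% | 3.8 | 1.56 |
| Insulin favorable, control failure | 24.25% | 238.28/700 = 34.04% | 9.8 | 4.03 |

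With whole subjects (170 and 217 favorable), the first three Z values are 2.83, 2.81 and 1.53.

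At a 25% control rate, the smallest observed difference that reaches Z = 2.02 is 5.0 points for both complete case and all failure. It is 8.2 points for the adverse arm-opposed assignment. Observed differences from 5.0 to about 8.1 points, including the 7-point design effect, pass the SAP's rule and fail that bound.

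**Tipping point.** Count all 21 missing insulin subjects as failures (217/700 favorable) and let k missing controls be favorable:
- k = 12: 182/700 against 217/700, Z = 2.07.
- k = 13: 183/700 against 217/700, Z = 2.01, below 2.02.

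With the unrounded counts the crossing comes at k = 14 (Z = 1.98).

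**Unequal splits of the 42 missing**
- 14 control/28 insulin, 25% vs 30%: all failure moves p from 0.040 to 0.070.
- 7/35, 25% vs 31%: Z goes from 2.46 to 1.98, below the boundary.
- 14/28, 25% vs 32%: Z = 2.57 under all failure, still significant. With all 42 missing on insulin, Z = 2.15.
- 28/14, 25% vs 30%: Z rises from 2.07 to 2.30. When more controls are missing, the rule labeled worst case favors insulin.

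**The case against.** **The rule is not inert.** It is nearly neutral only when missing rates are similar by arm. If insulin subjects are missing more often, it penalizes insulin and can turn a borderline result, as the 7/35 and 14/28 splits show. This stands. A reader might infer that the planned analyses agree by construction, or that they cannot detect that differential loss matters. The documents do not support either inference. What remains is that the rule responds to how many are missing in each arm. It does not respond to how the missing subjects' outcomes differ between arms.

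**The SAP does not say that agreement proves robustness.** It says that a robust effect should give similar results, which is the other direction. A reader might draw the converse, but the text does not state it.

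**There are other safeguards.** The review of reasons and patterns of missing data is a direct check for differential withdrawal, and discrepancies are to be investigated. The out-of-window analysis replaces some imputed values with observed ones. Complete case can differ from the multiple imputation, which also uses age, gender and 6-week mRS. All of this stands, but none of it bounds the effect on the treatment difference.

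**Differential loss may be small.** Treatment lasts at most 72 hours. Subjects are blinded, and the 6-week call and 90-day assessment are done by blinded investigators (Protocol 8.6). Stopping therapy does not stop follow-up (Protocol 9.1), and a telephone visit is allowed (Protocol 8.4). The pilot trials lost almost no one: none in one, and 99% with outcomes in the other (Protocol 3.4). This lowers the weight of the point without removing it.

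**The bound is extreme.** It needs every missing control to be favorable, against 25% assumed, and no missing insulin subject, against 32%. A strong but less extreme case, assumed for illustration, has 50% of missing controls and 16% of missing insulin subjects favorable. That gives 180.25/700 = 25.75% against 220.64/700 = 31.52%, Z about 2.39, still significant. This stands, and it is why the tipping point matters more than the bound.

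**Conclusion.** The point holds in a limited form. The all-failure analysis is mislabeled as a worst case for the comparison. With similar missingness by arm it moves Z only from 2.86 to 2.84, so its agreement with the primary result says little about outcomes missing not at random differently by arm. With more missing on insulin it can reveal fragility, but in no case does it bound the effect. At the planned 3% the arm-opposed bound takes Z to about 1.56, against a boundary of 2.02.

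It would be wrong to conclude that a 7-point result would probably be overturned. With every missing insulin subject failing, 13 of 21 missing controls (62%), or 14 on unrounded counts, would still have to be favorable, against 25% expected. The weight is moderate because expected missingness is low.

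The figures rest on equal arms of 700 despite response-adaptive allocation, an unadjusted test in place of the model with NIHSS strata and thrombolysis, complete case standing in for the multiple imputation, and assumed splits of the 42 missing outcomes.

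**What to change.** In SAP section 8:
1. Rename the existing analysis *all missing = failure* and keep it.
2. Add a tipping-point table for the primary outcome. Let the favorable rate among missing subjects vary separately in each arm from 0% to 100%. For each cell give the adjusted relative risk and the test statistic against the final boundary, and mark where the conclusion changes.
3. Make the two arm-opposed assignments the end points of the table: missing insulin not favorable with missing control favorable, and the reverse.
4. Report the number missing by arm beside the table, and state whether outcomes collected outside the window count as missing in it.
5. Say in advance that the table is judged by whether the tipping point is plausible, not by whether the extreme cell is significant.

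The cost is SAP wording and one table. No new data are needed, and the primary analysis and sample size do not change. The drawback is that the adverse extreme will often be non-significant, so it must be read with the tipping point.
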